## 8 Research Question and Objectives

Data in patients taking Yselty® in the real-world setting and for more than 1 year is needed to better understand certain safety parameters associated with long-term use. The overall study aim is to assess the long-term safety of Yselty® when used in real life clinical practice.

The primary objective is:

- **I.** To evaluate routinely collected data on long-term safety (>12 months) in relation to BMD with use of Yselty® 200 mg (with ABT) and 100 mg (with and without ABT) dosing regimens.

The exploratory objectives are:

- **II.a** To evaluate the incidence of osteoporosis or fractures suspected to be due to osteoporosis
- **II.b** To evaluate liver enzyme levels above the upper limit of normal and correlated events collected as part of clinical practice
- **II.c** To evaluate any routinely collected clinical data on mood disorders
- **II.d** To evaluate the incidence of uterine endometrial and mammary gland adenocarcinoma
- **II.e** To describe treatment patterns for Yselty® dosing regimens with and without ABT
- **II.f** To evaluate patient adherence to Yselty® treatment
- **II.g** To evaluate any routinely collected clinical data on cardiac disorders indicative for QT interval prolongation
- **II.h** To assess if physicians who prescribe Yselty® follow the summary of product characteristics (SmPC) recommendations including performance of annual dual-energy X-ray absorptiometry (DXA) scans and adherence to the requirement of not prescribing the Yselty® 200 mg regimen without concomitant ABT
- **II.i** To evaluate the incidence of adverse drug reactions (ADRs), serious adverse drug reactions (SADRs) and pregnancies (including pregnancy follow-up)
- **II.j** To evaluate BMD change in patients with routinely collected DXA scans at multiple timepoints to assess mean change of BMD z- and t-scores from baseline or 12-month assessment during long-term (>12 months) use of Yselty®.

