  - Incidence rate of adverse events regarding electrocardiogram (ECG) findings indicative of QT interval prolongation, according to the physician's information
- For objective **II.h**:
  - Frequency of use of DXA scans in defined time periods:
    - Among patients with >1-year treatment, the number and proportion of Yselyt® users who received at least 1 DXA scan between 10 months until 14 months
    - Among patients with >2-year treatment, the number and proportion of Yselyt® users who received at least 2 DXA scans between 10 months until 26 months
    - Among patients with >3-year treatment, the number and proportion of Yselyt® users who received at least 3 DXA scans between 10 months until 38 months
    - Among patients with ≥4-year treatment, the number and proportion of Yselyt® users who received at least 4 DXA scans between 10 months until end of study
  - Frequency of DXA scans prior to treatment initiation in patients at high risk for osteoporosis or bone loss

---

 Additional analyses on ADRs will be performed.

 The RMP (see 15.1) contains targeted follow-up questionnaires for these events. Physicians who report these events will be asked to fill the corresponding targeted follow-up questionnaire.

 The RMP (see 15.1) contains targeted follow-up questionnaires for these events. Physicians who report these events will be asked to fill the corresponding targeted follow-up questionnaire.

 High risk patients will be identified by their treating physician as described in section 9.2.1.

- Number and proportion of patients who received Yselty® at a dose of 200 mg for more than 6 months without concomitant prescriptions for ABT at suitable time periods (e.g., 3-month intervals)
- For objective **II.i**:
  - Incidence rate of ADRs
  - Incidence rate of SADR
- For objective **II.j**:
  - Mean absolute and relative change in density (g/cm^2) and absolute value and relative change of BMD z-score and t-score from baseline (for patients with baseline DXA scan as per routine clinical practice – per SmPC only recommended for patients at high risk for osteoporosis or bone loss)

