## **9.2 Setting**

### **9.2.1 Study Population**

Patients with documented uterine fibroids and symptoms such as HMB who are therapy-naïve to Yselty® and who meet the criteria defined in the SmPC for prescription in the respective country. Patients will be enrolled after the decision to treat with Yselty® has been made, or as soon as possible after the start of Yselty® treatment, however, not longer than 3 months after treatment initiation. The decision to treat with Yselty® will not be influenced by study inclusion.

No further selection criteria except for inclusion and exclusion criteria outlined below should be applied. Based on examination of patient enrolment using progress reports on recruitment, a Steering Committee (see section 9.8.1) will provide recommendations regarding modifications to the study conduct that might be introduced to maximise recruitment.

Physicians should identify patients at high risk for osteoporosis or BMD loss according to the SmPC and relevant local guidelines. Such risk factors include a history of a low trauma fracture or other risk factors for osteoporosis or bone loss (such as chronic alcohol and/or tobacco use, strong family history of osteoporosis, low body weight, chronic kidney

---

 High risk patients will be identified by their treating physician as described in section 9.2.1.

disease, and overactive parathyroid gland), including those taking medications that may affect BMD (e.g., systemic corticosteroids, anticonvulsants). A more extensive reference list of risk factors is provided available as a stand-alone document in section 15.1.

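### The year-2 to year-4 DXA adherence items do not require a scan in each year, and the year-1 to year-3 items admit patients before their scan window closes

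*Protocol*

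**What the plan says.** Section 8 sets objective II.h: whether prescribers follow the SmPC, "including performance of annual dual-energy X-ray absorptiometry (DXA) scans". Section 9.1.2 turns this into four items:

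- Year 1, patients treated for more than one year: "received at least 1 DXA scan between 10 months until 14 months".
- Year 2, "Among patients with >2-year treatment": "received at least 2 DXA scans between 10 months until 26 months".
- Year 3, patients treated for more than three years: "received at least 3 DXA scans between 10 months until 38 months".
- Year 4, patients treated for four years or longer: "received at least 4 DXA scans between 10 months until end of study".

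Sections 9.3.6 and 9.7.3.4 refer back to 9.1.2 for these periods. Under section 9.2.6, observation of a patient without BMD decrease or osteoporosis ends when she stops treatment.

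A separate II.h item concerns scans before treatment starts in high-risk patients. Its footnote reads: "High risk patients will be identified by their treating physician as described in section 9.2.1". Section 9.2.1 adds: "Physicians should identify patients at high risk for osteoporosis or BMD loss according to the SmPC and relevant local guidelines". For the same item, sections 9.3.6 and 9.7.3.4 describe the group as patients with risk factors.

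**The concern.** The objective asks about yearly scanning, but from year 2 on the items measure a running total. A cluster of scans early in treatment can meet the total while a later year has none, and the result would still be reported as adherence.

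The denominators create a second problem. A patient counts in the year-2 item once she passes 24 months, but has until month 26 to have her second scan. If she stops, or the study ends, at 24.5 months with the scan due at month 25, she is recorded as not having met the rule although her time had not run out.

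II.h is where the study reports on adherence to the label's bone monitoring. Section 9.9 says the main objective depends on how far physicians perform these scans, so the rates also help a reader judge how complete the BMD data are.

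For the pre-treatment item, two descriptions of the denominator can yield two different groups.

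**Working it through.** **The plan's own figures.** Table 2 in section 9.5 reproduces. Effective n = 1,000 × 0.8^k gives 800, 640, 512 and 409.6. The half-width 1.96 × √(0.025 × 0.975 / n) gives 1.08%, 1.21%, 1.35% and 1.51%, against the stated 1.10%, 1.20%, 1.35% and 1.50%. The protocol gives no figure for II.h itself.

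**Cumulative count.** The year-2 window is 26 − 10 = 16 months long and the year-3 window 38 − 10 = 28 months. Scan patterns were put through the protocol's year-2 rule, and through a comparator that asks for one scan in months 10–14 and one in months 22–26:

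| Scans at months | Gap | Protocol rule | One per window |
|---|---|---|---|
| 12, 24 | 12 | met | met |
| 11, 13 | 2 | met | not met |
| 15, 21 | 6 | met | not met |
| 14.5, 25.5 | 11 | met | not met |
| 9.5, 21.5 | 12 | not met | not met |

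Any patient who meets the comparator has two scans inside months 10–26 and so meets the protocol's rule. Against this comparator the count can only be higher.

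How much higher depends on scan behaviour that the protocol does not give. A simulation assumed that each annual scan is done with probability 0.5 to 0.9, that timing has an SD of 1 to 3 months, and that 0 to 20% of patients have an extra scan. The two rules then differ by 1.1 percentage points (23.9% against 22.8%) to 31.5 points (52.4% against 20.9%). The upper end partly reflects how strict ±2 months is when timing is loose. It is a disagreement between two rules, not an error measured against truth.

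**Unfinished windows.** Inputs: 20% yearly dropout (9.5); start Q1/Q2 2026, end Q3/Q4 2029 and recruitment of up to 18 months (section 6), hence 36 to 48 months of data collection; first dose up to 3 months before enrolment (9.2.1).

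Dropout alone, at a constant rate: 1 − 0.8^(2/12) = 3.65%. That is about 29 of 800, 23 of 640 and 19 of 512. At 10% yearly dropout it is 1.7%; at 40% it is 8.2%.

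Now add administrative study end. Assume uniform accrual over 18 months, and let T be the longest possible time since first dose (study length plus lag). Treatment time at study end is then uniform from T − 18 to T, and the unfinished share is

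1 − 0.9635 × P(end after window close) / P(end after entry time).

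| T (months) | Year 2 | Year 3 | Patients >3 years, per 1,000 |
|---|---|---|---|
| 36 | 1 − 0.9635 × 10/12 = 19.7% | group empty | 0 |
| 39 | 1 − 0.9635 × 13/15 = 16.5% | 1 − 0.9635 × 1/3 = 67.9% | 85 |
| 42 | 1 − 0.9635 × 16/18 = 14.4% | 1 − 0.9635 × 4/6 = 35.8% | 171 |
| 45 | 3.7% | 1 − 0.9635 × 7/9 = 25.1% | 256 |
| 48 | 3.7% | 1 − 0.9635 × 10/12 = 19.7% | 341 |
| 51 | 3.7% | 1 − 0.9635 × 13/15 = 16.5% | 427 |

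The last column is 512 × (T − 36)/18. The year-1 share stays at 3.7% throughout. The grid moves in 3-month steps; with T between 36 and 38 months nobody in the year-3 group could complete the window.

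**Year 4.** This window has no fixed end, so its length differs between patients. Patients reach 48 months only at T = 51, where they number 1,000 × 0.8^4 × 3/18 = 68 per 1,000. Prolonging data collection, which section 9.1 allows, would change this.

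**Pre-treatment item.** The footnote defines the group by the physician's identification; sections 9.3.6 and 9.7.3.4 define it by risk factors. Sections 9.3.2 and 9.3.3 already collect individual risk factors and BMD-relevant medication, and section 15.1 lists a stand-alone criteria document.

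**The case against.** The best defence is that visits follow routine practice without fixed dates, so a cumulative count is a reasonable tolerance: 14.5 and 25.5 months is sensible annual scanning, and strict windows reject it. This stands. It is a reason for a wider-window sensitivity analysis and for keeping the count as a supplement. It does not rescue a rule that accepts months 11 and 13. The plan uses a guard of this kind elsewhere: for BMD change under II.j, section 9.7.3.4 works with yearly time points of ±6 months and a six-month minimum between measurements.

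It can also be said that calculated variables are left to the SAP and that II.h is exploratory and descriptive. Both are true and limit the weight of the point. But the periods and denominators are fixed in 9.1.2, and the later sections refer back to it.

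A reader might infer four stronger things that the protocol does not support:

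- That the annual-scan items depend on the physician's view of risk. They do not use high-risk status; the footnote belongs to the pre-treatment item only.
- That an overlooked risk factor must drop out of the pre-treatment denominator. This follows from the footnote, but not from 9.3.6 or 9.7.3.4.
- That the unfinished shares are misclassification rates. A patient scanned at months 12 and 24 whose observation ends at month 25 is counted correctly.
- That year 1 has the counting defect. It is already a single 4-month window.

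**Conclusion.** The point holds for an exploratory, descriptive endpoint. The year-2, year-3 and year-4 items do not measure annual scanning, because they require neither a scan in each year nor a minimum gap. The year-1 to year-3 items can record a patient as non-adherent before her window closes.

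The share with an unfinished window is about 3.7% at year 1, roughly 4–20% at year 2 and 16–68% at year 3 where that group is not empty. These ranges rest on 20% yearly dropout at a constant rate, uniform 18-month accrual, 36 to 48 months of data collection, an enrolment lag of 0 or 3 months, and exit from observation at dropout. Patients kept under observation after a BMD decrease would lower them a little.

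The first defect raises the reported rate and the second lowers it, by amounts that the protocol does not allow one to estimate. The rate therefore cannot be read as an upper or a lower bound. The pre-treatment item has a wording conflict whose size cannot be derived either. The primary endpoint uses available z-scores in patients treated beyond 12 months (9.7.3.3) and is not affected by these windows.

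**What to change.** In section 9.1.2:

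1. Limit each denominator to patients treated and observed to the end of the window concerned.
2. Report, for each treatment year, whether at least one scan was done, in non-overlapping windows such as months 10–14, 22–26 and 34–38.
3. Add a wider-window sensitivity analysis, for example the ±6 months and six-month minimum gap already used for II.j. It would accept 9.5 and 21.5 months, which the narrow windows still reject, and it would reject 11 and 13. It would also accept 15 and 21, and its windows close later, at 18, 30 and 42 months.
4. Keep the cumulative count as a supplement and tabulate the gaps between consecutive scans.
5. For the pre-treatment item, reconcile the footnote with 9.3.6 and 9.7.3.4: derive the group from the risk factors and medication recorded in the eCRF, and show the physician-identified group as a second version. Recorded risk factors are also entered by the sites, so this reduces the dependence on the physician without removing it.

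The cost is wording and programming, with no new data. Denominators become smaller, notably at year 3, where on the tabulated timelines 16–68% of the group would be excluded.

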  - Mean absolute and relative change in density (g/cm^2) and absolute value and relative change of BMD z-score and t-score from DXA scan at 12 months (for patients with multiple follow-up DXA scans as per routine clinical practice)

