### **9.5 Study Size**

Approximately 1,000 women of reproductive age with documented uterine fibroids and symptoms such as HMB being treated with Yselyt® long-term, according to the SmPC. This is a multinational study in 5 European countries (Germany, Italy, Spain, Poland and UK), whereas the selection and sequence of countries may change depending on the launch dates of Yselyt®. The number of study sites will vary per country, dependent on use of Yselyt®.

This is a descriptive study and is not intended to test a formal hypothesis. The sample size is based on feasibility and practical considerations rather than statistical. Sample size considerations are based on the primary endpoint, BMD z-score, which compares bone mineral density with a reference population of the same age and sex. The BMD z-score will

---

 Special situations include drug interactions, medication abuse, medication misuse, medication overdose, medication errors, unexpected therapeutic or clinical benefit from product use, pregnancy or lactation exposure with the product, lack of efficacy, off-label use, and occupational exposure (see section 11.4).

be measured at 3 sites for each patient, i.e., lumbar spine, total hip, and femoral neck and the lowest individual value is used to estimate the population proportion.

A single-group design was used to obtain a 2-sided 95% confidence interval (CI) for a single proportion. Given the standard normal distribution of BMD z-scores (z-distribution), the expected sample proportion of values < -2 (cutoff for low bone density) is assumed to be 2.5%, which corresponds to the lower 2.5% quantile of the z-distribution. With an effective sample size of 800 (assuming 20% dropout), the CI width at 12 months of follow-up is 2.2% and the expected precision of the proportion is 2.5%±1.1% (see Table 2). Assuming a further 20% yearly dropout rate, at 24 months of follow-up, the effective sample size is estimated to be 640 patients with a CI width of 2.4% and an expected precision of the proportion of 2.5%±1.2%. At 36 months of follow-up, the effective sample size is estimated to be 512 patients with a CI width of 2.8% and an expected precision of the proportion of 2.5%±1.4%. At 48 months of follow-up, the effective sample size is estimated to be 409 patients with a CI width of 3.0% and an expected precision of the proportion of 2.5%±1.5%.

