BMD will be displayed as absolute and relative change in density ( $\text{g}/\text{cm}^2$ ) and absolute value and relative change of z-scores and t-scores over time by means of summary statistics; e.g., DXA scans performed at baseline (if available) vs. timepoint 1 – 1st year (+/-6 months) after treatment initiation, timepoint 1 – 1st year (+/-6 months) after treatment initiation vs. DXA scans performed at timepoint 2 – 2nd year (+/-6 months), where the measurements are at least 6 months apart. This is continued in the same way for further years if the sample size is at least 5 patients. Changes are only analysed if e.g., the machine types, the location of the scan and other criteria that allow comparability are consistent. A subgroup analysis of t-scores for the subgroup of postmenopausal patients and of z-scores in the subgroup of premenopausal patients will be conducted, if sample size allows. Additionally, patients who experienced BMD decrease during the study but continued to be observed in the study, regardless of the reason for which Yselty® treatment was discontinued, will be investigated as a separate subgroup. This subgroup analysis will include the presentation of both absolute value and relative change of z-scores and t-scores after discontinuation. If the sample size permits, this subgroup will be stratified based on whether alternative treatments administered after discontinuation may also lead to a decrease in BMD (refer to “previous systemic treatments” in section 9.3.3).

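### Objective II.j specifies relative change for BMD z- and t-scores, a ratio that is undefined at zero and reverses sign below zero, and does not name their absolute change

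*Protocol*

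**What the plan says.** Section 8 of the Protocol sets exploratory objective II.j "to assess mean change of BMD z- and t-scores from baseline or 12-month assessment". It does not say relative change.

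Section 9.1.2 turns this into two endpoint bullets. For density, each opens with "Mean absolute and relative change in density". For the scores, the first continues with "absolute value and relative change of BMD z-score and t-score from baseline" and the second with "absolute value and relative change of BMD z-score and t-score from DXA scan at 12 months".

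Section 9.7.3.4 repeats the pairing in the main II.j analysis: "absolute value and relative change of z-scores and t-scores over time by means of summary statistics". For patients with a BMD decrease who are followed after stopping treatment, it adds: "This subgroup analysis will include the presentation of both absolute value and relative change of z-scores and t-scores after discontinuation". That sentence does not mention density.

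Section 9.5 describes how z-scores are taken to be distributed: "Given the standard normal distribution of BMD z-scores (z-distribution". That distribution is centred on zero.

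Section 9.7.1 has a general rule that continuous variables are summarised by their values and, where applicable, by changes from baseline. The planned statistics include both mean and median. The Protocol does not define relative change, and it makes no provision for a reference score that is zero or negative.

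**The concern.** A percentage change needs a scale with a true zero and positive values. Density in g/cm² has both. A z- or t-score is a signed deviation from a reference population, so its zero is only the reference mean. Dividing by such a score gives no result at zero, very large results near zero, and the opposite sign below zero. A woman who goes from −1.0 to −1.3 has lost bone, yet her relative change is +30%.

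The study exists to describe BMD under long-term use, and II.j is the objective that quantifies change. A table of mean or median percentage change in z-score could show the wrong direction. The subgroup followed after discontinuation is the most exposed, because it is selected for a BMD decrease and its output sentence names no change measure that works. There a recovery from −1.0 to −0.7 would be shown as (−0.7 + 1.0)/(−1.0) = −30%.

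**Working it through.** The Protocol gives no numerical result to reproduce here. The check concerns a property of the scale.

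**Inputs from the Protocol.** Reference z-scores are N(0,1) (section 9.5). Relative change of z- and t-scores is specified from baseline and from the 12-month scan (9.1.2, 9.7.3.4). Yearly comparisons continue with as few as 5 patients (9.7.3.4). Baseline scans are recommended only for high-risk patients (9.1.2).

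**Assumptions.** Relative change = 100 × (follow-up − reference)/reference. The loss of 0.3 score units is illustrative.

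**Step 1: the same loss at different reference values.**

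| Reference | Follow-up | Relative change |
|---|---|---|
| +1.0 | +0.7 | −30% |
| +0.1 | −0.2 | −300% |
| 0 | −0.3 | undefined |
| −0.1 | −0.4 | +300% |
| −0.5 | −0.8 | +60% |
| −1.0 | −1.3 | +30% |

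Take the five defined rows as five patients, the smallest sample for which yearly comparisons continue. The mean is (−30 − 300 + 300 + 60 + 30)/5 = +12% and the median is +30%. Every one of them lost 0.3 units.

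**Step 2: how often this arises.** Under N(0,1), 50% of references are negative, 8.0% lie within ±0.1, and 4.0% round to 0.0 at one decimal. With a mean of −0.5 (assumed), 69% are negative. With a mean of −1.0 (assumed), 84% are negative.

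**Step 3: direction of the median.** If every patient loses bone, the share with a positive relative change equals the share with a negative reference: 50%, 69% or 84%. This needs no assumption about the size of the loss. Once the share exceeds half, the median is positive. If changes are instead N(−0.3, 0.3²), so that 84.1% of patients lose bone, the shares are:

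- mean 0: 50%
- mean −0.5: 0.841 × 0.691 + 0.159 × 0.309 = 63%
- mean −1.0: 0.841 × 0.841 + 0.159 × 0.159 = 73%

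**Step 4: simulation.** 4,000 samples of n = 100, with change N(−0.3, 0.3²), which is assumed.

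| Reference mean | Median relative change (central 95% of samples) | Samples with positive mean relative change | Mean absolute change (central 95%) |
|---|---|---|---|
| 0 | 0% (−15 to +16) | 49% | −0.36 to −0.24 |
| −0.5 | +15% (+4 to +26) | 60% | −0.36 to −0.24 |
| −1.0 | +19% (+12 to +27) | 72% | −0.36 to −0.24 |

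The spread of the mean relative change should not be quoted as a fixed size. Under this model the ratio has no finite expectation, so its range depends on the run. With loss 0.3, SD 0.2 and n = 300, two runs differing only in the random seed gave −650% to +454% and −508% to +470%. A larger sample does not help: at reference mean 0 the range was −541% to +580% at n = 100 and −635% to +662% at n = 400.

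**Step 5: the alternatives.** Absolute score change recovers the loss in every scenario above. Relative change in density also behaves well. Assuming baseline 1.0 g/cm² (SD 0.12) and loss 0.036 (SD 0.036), it is about −3.7%, with a range of −4.4% to −2.9% at n = 100.

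**The case against.** The strongest reply is that little is lost. The same bullets report absolute and relative change in density, which measures bone loss directly, and they show the score values by time point. Section 9.7.3.3 adds shift tables where results can be categorised. The general rule in 9.7.1 already allows change from baseline for continuous variables. The formula for relative change is not given and could be settled in the SAP. II.j is one of ten exploratory objectives in a descriptive study.

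Most of this stands, and it limits the point. It does not remove it:

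- The rule in 9.7.1 applies only where applicable, does not expressly cover the 12-month reference, and does not cancel the relative change that 9.1.2 and 9.7.3.4 require.
- The SAP could choose a formula, but none rescues the ratio. Dividing by the absolute value of the reference restores the sign, yet a 0.3 loss from ±0.01 is still −3000%.
- The wording about values may be a slip for absolute change. If so, the text should be corrected, because it appears in all four places and density is worded differently in the same bullets.
- The subgroup sentence lists what the analysis will include, so it does not exclude density. It does not call for it either.

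It is also fair that N(0,1) is a sample-size assumption, not a description of the women who will have a reference scan. The Protocol gives no figures for them and no distribution for t-scores. That is why reference means of 0, −0.5 and −1.0 are shown side by side.

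**Conclusion.** The wording is wrong as it stands. Relative change is not a usable summary of z- or t-scores, and the change measure that objective II.j asks for is not named for the scores in its endpoint or analysis text. The sign reversal and the failure at zero are algebra and need only the natural reading of relative change. The claim that the median also points the wrong way rests on a further assumption, that most reference scores are negative. This is plausible for baseline scans, which are recommended only for high-risk patients, but the documents do not establish it.

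A reader might infer that II.j as a whole cannot be interpreted, or that the study loses its measure of bone loss. The documents do not support that. Density change and score values by time point remain sound, and the primary endpoint, the proportion with a z-score below −2, does not use relative change. Only the relative-change summaries of the scores fail, with most effect in the post-discontinuation subgroup. For an exploratory objective this is minor to moderate.

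**What to change.** 1. In both II.j bullets of section 9.1.2 and in the main II.j sentence of section 9.7.3.4, specify for z- and t-scores the absolute value and the absolute change, defined as follow-up minus reference in score units.
2. Keep relative (percentage) change for density in g/cm² only.
3. In the post-discontinuation sentence of 9.7.3.4, make the same replacement for the scores and add absolute and relative change in density.

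The cost is rewording in four places and dropping an uninterpretable table column. No new data are needed, because density values are already collected under Table 1 and section 9.3.6. Sample size and the primary analysis do not change. Confidence intervals for the score changes could be added but are not needed to cure the defect.
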